## SECTION 1: DEMOGRAPHICS

1.1 What is your gender?      Male      Female

1.2 How old are you? \_\_\_\_\_ (age in years)

1.3 What town do you live in?

Frazer  
Oswego  
Wolf Point  
Poplar  
Brockton  
Fort Kipp  
Other \_\_\_\_\_

1.4 What grade are you in?

9th  
10th  
11th  
12th

## SECTION 2: CULTURAL IDENTITY (*tertiary outcome variable*)

The next set of questions are related to your culture and what it means for you to be an American Indian.

2.1 How much do you now live by or follow an American Indian way of life?

- a. Not at all
- b. A little
- c. Some
- d. A lot

2.2 How much do you now live by or follow a White or Anglo way of life?

- a. Not at all
- b. A little
- c. Some
- d. A lot

2.3 How important is it to you to follow religious or spiritual beliefs which are based on traditional Indian beliefs?

- a. Not at all important
- b. Not very important

- c. Somewhat important
- d. Very important

2.4 How important is it to you to follow religious or spiritual beliefs that are based on Christian beliefs such as Catholic, Baptist, Mormon, etc.?

- a. Not at all important
- b. Not very important
- c. Somewhat important
- d. Very important

2.7. How proud are you to be an American Indian?

- a. Not at all proud
- b. Not very proud
- c. Somewhat proud
- d. Very proud
- e. I do not consider myself to be an American Indian.

2.8 What kinds of activities have you participated in over the past year?

 Gathering traditional foods	 Singing and drumming
 Beading	 Traditional ceremonies
 Hand/stick games	 Sweats
 Hunting	 Kinship History
 Using sacred medicine	 Going to Pow Wows
 Dancing at Pow Wows	 Learning what it means to be a
 Traditional beliefs about sex	man (if male)/woman(if female)
 Learning about what it means to be an adult	
 Sundance/Medicine lodge	
 Other (please describe):	

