**Table 1. Overview of *NIE*'s 9-month multi-level, multi-component intervention plan.**

INDIVIDUAL	FAMILY	COMMUNITY	SYSTEMS
Native Stand (NS): 18-session school-based curriculum delivered twice a month over 9 months in NIE 's 5 participating schools. NS will be integrated into the schools' existing class schedules.	Native Voices (NV): 4 sessions delivered once every other month to students and parents/legal guardians after school hours at NIE 's 5 participating schools.	Cultural Mentoring Program (CMP): 9 mentoring sessions delivered twice a month over 9 months that include one group activity with CMP mentors and mentees and one 1:1 meeting. CMP activities will take place at varying locations on the Reservation depending on the activity.	SRH Services: Monthly meetings over 12 months with Epi Team at the Fort Peck Tribes Headquarters offices in Poplar, Montana.
NS 1: Introduction to an overview of NIE and Native Stand	NV 1: Introduction to an overview of NIE and Native Voices	CMP 1: Assiniboine/Sioux kinship networks and concepts of family and genealogy	Epi Team meetings will take place monthly over 9 months to enhance coordination and implementation of SRH services for AI youth.
NS 2: Culture & Tradition – Part 1		CMP 2: Traditional male/female roles and cultural beliefs about healthy relationships	
NS 3: Culture & Tradition – Part 2		CMP 3: Cultural beliefs about sex and how to make decisions about sex that integrate cultural values	
NS 4: Healthy Relationships – Part 1		CMP 4: Cultural beliefs about parenting and the role of family	
NS 5: Healthy Relationships – Part 2		CMP 5: The role of ceremony in traditional Assiniboine/Sioux culture	
NS 6: Reproductive Health – Part 1		CMP 6: The role of sweat lodges in AI spirituality	
NS 7: Reproductive Health – Part 2		CMP 7: Honoring ceremonies in the lives of young men and women	
NS 8: Pregnancy & Parenting		CMP 8: Understanding the sacredness of the land	
NS 9: Preventing Pregnancy		CMP 9: Buffalo Harvest	
NS 10: Condoms & Birth Control			
NS 11: Sexually Transmitted Diseases			
NS 12: HIV/AIDS & HCV			
NS 13: Drugs, Alcohol, & Sex	NV 3: Prevention of STIs, HIV/AIDS, and HCV		
NS 14: Mental Health & Sex			
NS 15: Negotiation & Refusal Skills			
NS 16: Decision-Making			
NS 17: Effective Communication			
NS 18: Putting It All Together			

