### **6.3.2. List of Data Source Materials and Measures (Table 2 below).**

**Student Survey:** To assess students' participation in N/E, we draw from several existing measurements that have been implemented and validated in research studies with AI youth. Primary outcome measure: Condom use will measure frequency of condom use relative to frequency of sex during sexual intercourse using questions derived from the Risk Behavior Assessment. Secondary outcome measures: These will include the number of sex partners; age of onset of sexual intercourse; frequency of sexual intercourse; pregnancy history; frequency and type of birth control used during sexual intercourse relative to the frequency of sexual intercourse; and frequency and types of substance use (cigarettes, marijuana, alcohol, and methamphetamine). Tertiary outcome measures: Parent/legal guardian communication is measured by the frequency and types of SRH topics that parent/legal guardian and child discussed. Cultural identity is measured using two established measurements: One measure assesses the extent to which a student identifies with his or her American Indian culture and feels cultural pride, and the other measure assesses frequency and type of participation in cultural activities. Access to SRH services is measured by frequency and type of SRH service used (ever been tested for STIs and follow-up, ever been tested for HIV and follow-up, ever been tested for HCV and follow-up, ever been pregnant/gotten someone pregnant and follow-up). Other variables to be measured in N/E that assess attitudes, intentions, skills, and mental health are: Motivation to avoid STIs, HIV, HCV, and pregnancy, as measured by asking students how important it is to them to keep themselves (or someone else) from getting an STI, HIV, and HCV, and how important it is to them to keep from getting pregnant or getting someone pregnant. Intention to use condoms and/or birth control is measured by asking students how likely it is they will use condoms and/or birth control the next time they have sexual intercourse. Intention to abstain from sex is measured by asking students how likely it is that they will not participate in sexual intercourse. Condom and birth control use self-efficacy is measured by assessing confidence in one's ability to use condoms and birth control. Refusal skills regarding sex are assessed by how strongly students believe they can say no to sex. Knowledge about STIs, HIV, HCV, pregnancy, and healthy relationship characteristics are measured using true/false/don't know questions. Mental health is assessed using two established measures: One measure assesses depression using the C-ESD, and the other measurement assesses exposures to stressful life events by assessing lifetime occurrences of a series of negative events. Standard demographic measures in the student survey are age, gender, sexual orientation, school, and highest grade completed.

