**Table 2. NIE Measures.**

**Table 2. N/E Measures.**

Data Collection Instruments and Measures	Data Collection: Baseline & Months				Description of Measures Number of Items; Scale Anchors; Benchmark Values	
	Base	3	9	12		
Student Survey						
Primary Outcome Variable						
Proportion of condom use during sexual intercourse (SI)	X	X	X	X	2 items; number of times condom used relative to number of times had SI	
Secondary Outcome Variables						
Age of onset of sexual intercourse	X	X	X	X	2 items; ever had SI & age at first SI	
Number of sex partners	X	X	X	X	2 items; lifetime & past-month sex partners	
Frequency of sexual intercourse	X	X	X	X	1 item; frequency of SI in past month	
Pregnancy history	X	X	X	X	1 item; number of pregnancies	
Type & frequency of birth control (BC) during sexual intercourse	X	X	X	X	3 items; type of BC use and number of times BC used during SI	
Type & frequency of substance use (SU) during sexual intercourse	X	X	X	X	1 item measures SU with SI; 5 items measure lifetime and past month SU	
Tertiary Outcome Variables						
Type & frequency of parent/legal guardian-child SRH communication	X	X	X	X	24 items Likert scale; higher score = higher communication	
Cultural identity & participation in cultural activities	X	X	X	X	3 items cultural identity ( $\alpha = .75$ ); 2 items cultural activities engagement ( $\alpha = .46$ )	
Type & frequency of SRH services	X	X	X	X	9 items; frequency, type, and follow-up of SRH services used	
Other Variables						
Motivation to avoid STIs, HIV, HCV, & pregnancy	X	X	X	X	Up to 9 items; 1 (very true) to 5 (very untrue); 1 = more positive attitude/motivation	
Condom & birth control use intention & self-efficacy	X	X	X	X	4 items per intention; 1 (very true) to 5 (very untrue); 1 = higher intention; 6 self-efficacy items; 1 (very easy) to 4 (very hard); 1 = high self-efficacy	
Abstinence	X	X	X	X	3 items; 1 (strongly disagree) to 4 (strongly agree); 4 = more supportive of teen abstinence	
Refusal skills regarding sex	X	X	X	X	7 items; 1 (I definitely can say no) to 5 (I definitely can't); 1 = stronger refusal skills	
Knowledge of STIs, HIV, HCV, pregnancy, & health relationships	X	X	X	X	Range of 4 to 10 items per topic; True/False/DK; Average proportion of questions correct	
Depression (CES-D) & exposure to stressful life events	X	X	X	X	CES-D — 7 items ( $\alpha = .80$ ); Life Events — 24 items; Yes/No; number of events observed	
Student Demographics						

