H1: AI youth who participate in N/E will demonstrate increased condom use at 3, 9, and 12 months. (12 months will be used in the Primary Outcome analysis; 3 and 9 months will be used in the Secondary Outcomes analysis.) H2: AI youth who participate in N/E will demonstrate increased use of other birth control at 3, 9, and 12 months. They also will demonstrate a decrease in sexual risk behaviors as measured by reduced number of sex partners, delayed onset of sexual intercourse, and decreased substance use during sex, at 3, 9, and 12 months. (Secondary Outcomes) H3: N/E parents/legal guardians and youth will demonstrate significantly increased communication about topics related to SRH at 3, 9, and 12 months. AI youth who participate in the cultural mentoring program will demonstrate significantly increased understanding of cultural values related to traditional AI beliefs regarding SRH at 3, 9, and 12 months. And AI youth who participate in N/E will report significantly increased use of SRH services at 3, 9, and 12 months as a result of improved coordination among education, health care, and social service agencies on the Fort Peck Reservation. (Tertiary Outcomes) AIM 3: Evaluate the fidelity and acceptability of N/E. N/E's fidelity and acceptability will be evaluated using qualitative methods, including focus groups, activity logs, and staff field notes and meetings.

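### H3 claims a gain in understanding of cultural values about SRH, but its measures cover only identity and participation, and three to five boxes of the activity list overlap with the mentoring syllabus

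*Combined protocol and SAP*

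**What the plan says.** The cultural part of H3, stated for all three follow-up surveys in the Study Description of the appended registration record, reads: "AI youth who participate in the cultural mentoring program will demonstrate significantly increased understanding of cultural values related to traditional AI beliefs regarding SRH". Section 2.3.2 names the same construct among the tertiary outcomes of Aim 2.

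Section 6.3.2 describes two cultural measures. One asks how far the student "identifies with his or her American Indian culture and feels cultural pride"; "the other measure assesses frequency and type of participation in cultural activities". Table 2 labels the outcome "Cultural identity & participation in cultural activities" and lists 3 identity items (alpha .75) and "2 items cultural activities engagement" (alpha .46).

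Section 2 of the student survey prints items 2.1 to 2.4 (way of life, importance of spiritual beliefs), 2.7 (pride) and 2.8. Item 2.8 asks "What kinds of activities have you participated in over the past year" and offers 15 named tick boxes plus an open Other.

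Table 1 lists nine mentoring sessions over nine months, for example "CMP 6: The role of sweat lodges in AI spirituality". Section 3.1.3 defines dose from the components delivered to each student, allowing for attendance and participation. The mixed-model section (second 3.1.5) treats tertiary outcomes as continuous and lets the intervention term be either 0/1 or a dose representation.

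**The concern.** There are two linked problems.

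First, the hypothesis and the measure are different constructs. A student can feel prouder, or take part in more activities, without understanding traditional values about SRH any better, and the reverse is also possible. If the plan is followed as written, a rise on identity or participation items would be reported as a gain in understanding.

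Second, some boxes in item 2.8 describe what the mentoring sessions teach. A student who attends those sessions can truthfully tick them with nothing else in his or her life having changed. To that extent the item records receipt of the intervention, and a positive result is partly circular. If the model uses the dose form of the intervention term, attendance is regressed in part on itself.

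At stake is a tertiary claim. It matters because the long-term goal in Section 2.3.2 is a toolkit for other tribal communities that includes the mentoring programme.

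**Working it through.** The plan gives no effect size, SD or power for the cultural outcome, so there is no figure to reproduce. The check sets the texts side by side and then sizes the overlap.

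**Step 1: does any item test understanding?** The identity items and item 2.8 do not. The knowledge scales in Section 6.3.2 and Table 2 cover STIs, HIV, HCV, pregnancy and healthy relationships, not cultural values. The one cultural box about sex in item 2.8 records participation. Survey numbering jumps from 2.4 to 2.7, but Table 2 allows only identity or activity items there. Items that test understanding of cultural values about SRH: 0.

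**Step 2: match item 2.8 to the mentoring sessions in Table 1.**

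| Option in 2.8 | Session | Match |
|---|---|---|
| Kinship History | CMP 1 | direct |
| Learning to be a man/woman | CMP 2 | direct |
| Traditional beliefs about sex | CMP 3 | direct |
| Traditional ceremonies | CMP 5, CMP 7 | probable |
| Sweats | CMP 6 | probable |
| Hunting; gathering foods | CMP 9 | possible |
| Learning to be an adult | no single session | possible |

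That makes 3 direct, 3 + 2 = 5 with probable matches, and 5 + 3 = 8 with possible ones. The other 15 − 8 = 7 (two pow wow boxes, beading, singing and drumming, hand games, sacred medicine, Sundance) have no listed session.

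**Step 3: recall window.** The programme runs 9 months. A past-year window covers about 3 months of it at the 3-month survey, and all or nearly all of it at 9 and 12 months. The stem does not exclude N/E activities.

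**Step 4: illustrative size.** The documents give no scoring rule. Assume a count of m = 15 boxes, a baseline tick rate p of 0.2 to 0.6, an inter-item correlation r of 0 to 0.4, and a share a of 50% to 100% of mentored students who tick a matching box because of a session. None of these values is in the documents. With k matching boxes:

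- shift = k × (1 − p) × a
- SD = √[m p (1 − p)(1 + (m − 1) r)]

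Using only the direct matches (k = 3):

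- Smallest in SD units (p = 0.6, r = 0.4, a = 0.5): shift = 3 × 0.4 × 0.5 = 0.6; SD = √(15 × 0.24 × 6.6) = 4.87; ratio 0.12.
- Middle (p = 0.4, r = 0.2, a = 1): shift = 3 × 0.6 × 1 = 1.8; SD = √(15 × 0.24 × 3.8) = 3.70; ratio 0.49.
- Largest (p = 0.2, r = 0, a = 1): shift = 3 × 0.8 × 1 = 2.4; SD = √(15 × 0.16) = 1.55; ratio 1.55.

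With the two probable matches added (k = 5), the middle case is 3.0 boxes, or 0.81 SD.

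**The case against.** The best defence is that Table 2 already labels the outcome accurately as identity and participation, that it is tertiary, and that the outcome list in the appended registration record omits it. On that view the fault is one loose word in H3. This stands as a limit on importance, but H3 and Aim 2 are the statements against which results will be read, and both say understanding.

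A second defence is that cultural activity reached through a mentor is still genuine participation. That is fair, but it is also exposure, which Section 3.1.3 already tracks as dose. It cannot serve as independent evidence of benefit.

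A reader might go further in three ways that the documents do not support:

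- *That the whole cultural outcome is an attendance count.* The identity and pride items are not attendance, seven boxes have no listed session, and counting is an assumption. Section 6.3.2 speaks of frequency and type, while the printed tick list records type only.
- *That at least five boxes match, so attendance adds about five.* Only three matches are direct. The sessions on ceremony and sweat lodges are titled by topic, and nothing says that students take part in either. A gain of five also needs every student to start with none of the five ticked. Section 2.3.4 says the mentoring programme has existed for five years, so some will be ticked at baseline.
- *That alpha .46 shrinks the effect by √0.46 = 0.68 and requires 1/0.46 = 2.2 times the sample.* In Table 2 that alpha belongs to a two-item scale. The survey prints one activity item with 15 boxes, and nothing shows that the .46 describes it.

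**Conclusion.** The concern holds in two limited parts. The mismatch between the claimed construct and its measures is plain from the text and needs no assumption: no item tests understanding of cultural values about SRH. The contamination affects only the activity part: three of 15 named boxes directly, five with probable matches. Its size cannot be fixed from the documents. Under the stated assumptions, including a simple count, attendance alone could move the score by 0.6 to 2.4 boxes (0.12 to 1.55 SD) from the direct matches, which is enough to produce an apparent effect. The identity items are not affected by this overlap, and neither is the primary outcome. This is a worthwhile, low-severity correction.

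**What to change.** 1. Reword the cultural claim in H3, and the matching phrase in Aim 2, to cultural identity and participation in cultural activities.
2. Make the 3-item identity scale (alpha .75) the main cultural outcome and name its items. The survey prints five candidates (2.1 to 2.4 and 2.7), so the plan must say which three.
3. Before analysis, state the scoring rule for item 2.8 and list the boxes judged to match mentoring sessions. Score participation from the rest: 12 boxes if only the direct matches are removed, 10 if the probable ones go too. Analyse the matching boxes with the dose and fidelity data.
4. Do this at the analysis stage. Section 4.1 schedules baseline for March to June 2019; if it has been collected, leave the stem of 2.8 unchanged, because new wording would make later waves incomparable with baseline.

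If the team wishes to keep the claim about understanding, it needs a short scale that tests it, developed with the community advisory board. Added after baseline, such a scale would have no baseline value.

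Steps 1 to 3 need no new data collection. The cost is a text change, with whatever advisory board and IRB review that requires, a narrower tertiary claim and a shorter activity list.

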### **SECTION 3: COMMUNICATION ABOUT SEX WITH PARENTS/LEGAL GUARDIAN** (*tertiary outcome variable*)

Now you are going to be asked questions about what kinds of topics related to sex you do or do not talk with your parents/legal guardian about.

3.1. Have you talked with your parent/legal guardian about each of the following topics in the past year?

	.	YES	NO	I DON'T KNOW
a. What qualities are important in choosing close friends				
b. What qualities to look for in a boyfriend/girlfriend/life partner				
c. How boys' bodies change physically as they grow up				
d. How girls' bodies change physically as they grow up				
e. How women get pregnant and have babies				
f. Symptoms of sexually transmitted infections (STIs)				
g. Reasons why people like to have sex				

h. How well birth control can prevent pregnancy			
i. How to choose a method of birth control			
j. How to say no if someone wants to have sex and you don't want to			
k. How well condoms can prevent sexually transmitted infections (STIs)			
l. Menstruation (having menstrual periods)			
m. The importance of not pressuring other people to have sex			
n. How you will make decisions about whether or not to have sex			
o. Consequences of getting pregnant/getting someone pregnant			
p. How to use a condom			
q. Reasons why you should not have sex			
r. Masturbation			
s. What it feels like to have sex			
t. Homosexuality/people being gay			
u. Wet dreams measured for boys only			
v. What to do if a partner doesn't want to use a condom			
w. How people can prevent getting sexually transmitted infections (STIs)			
x. How you will know if you are in love			

#### **SECTION 4: ACCESS TO REPRODUCTIVE HEALTH SERVICES(tertiary outcome variable)**

This next set of questions is about where you go to get services like getting a pregnancy test, sexually transmitted disease test, or birth control.

4.1 Have you ever been to Indian Health Service or Fort Peck Tribal Health for things like condoms, birth control, a pregnancy test or a sexually transmitted disease test?

- a. yes
- b. no

4.2 If you need to get condoms, birth control, a pregnancy test, or a sexually transmitted disease test, where would you go? (Mark all that apply)

- a. Indian Health Services
- b. Fort Peck Tribal Health
- c. Roosevelt County Health Department
- d. Somewhere off the reservation
- e. The Hospital
- f. A private doctor
- g. Local stores
- h. School nurse
- i. Teachers or counselors in your school
- j. Elder
- k. Other

4.3 If you had to put your response on a scale, how uncomfortable or comfortable would you say you feel when a health care provider talks with you about birth control and STDs? Would you say you are:

- a. Very uncomfortable
- b. Slightly uncomfortable
- c. Neither uncomfortable or comfortable

- d. Slightly comfortable
- e. Very comfortable

4.4 In general, how satisfied or dissatisfied would you say you are with the birth control and STD information and services you have received from health care providers in the past?

- a. Very dissatisfied
- b. Somewhat dissatisfied
- c. Neither satisfied nor dissatisfied
- d. Somewhat satisfied
- e. Very satisfied

4.5 How likely is it that you will seek birth control or STD services from a health care provider in the next year?

- a. Not at all likely
- b. A little likely
- c. Moderately likely
- d. Very likely
- e. Extremely likely

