**4) Systems Level.** The fourth level of our study is a community-level strategy that involves mobilizing a network of education, health care, and social service agencies at Fort Peck to coordinate reproductive health services for 15- to 18-year-old AI youth over a 12-month period. The systems-level approach will utilize existing tribal infrastructure by enhancing the work of the established Fort Peck Tribal Epidemiology Team (Epi Team). The Epi Team is a local committee made up of the Fort Peck Tribal Health Department; Indian Health Service (Poplar Service Unit and Wolf Point Service Unit); the Roosevelt County Health Department; and school nurses from the Fort Peck Health Promotion and Disease Prevention Program. The Epi Team meets monthly and has been in existence for 15 years with the purpose of monitoring diseases on the reservation and the health status of the Assiniboine and Sioux tribes. As part of N/E, the Epi Team is tasked with improving the coordination and implementation of STI, HIV, and HCV screening, condom distribution, contraceptive services, and pregnancy testing on the Fort Peck Reservation.

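### The student survey asks about past use of contraception and pregnancy-test services at two agencies only, as a lifetime yes/no, so this part of H3 and its promised frequency cannot be measured

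*Combined protocol and SAP*

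**What the plan says.** The registry text (Study Description, H3) expects greater use of SRH services "as a result of improved coordination among education, health care, and social service agencies on the Fort Peck Reservation". The fourth level of the intervention works through the Epi Team. Section 6.3, Systems Level, lists as members the Tribal Health Department, Indian Health Service, "the Roosevelt County Health Department; and school nurses from the Fort Peck Health Promotion and Disease Prevention Program". The footnote to Section 2.3.4 adds the five high schools. Condom distribution, contraceptive services and pregnancy testing are among the services the team is to coordinate.

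Table 2 describes the tertiary service-use measure as "9 items; frequency, type, and follow-up of SRH services used", and outcome 9 of the registry text says the same. Section 6.3.2 explains it through STI, HIV and HCV testing, pregnancy, and follow-up. No document identifies the nine items or gives a scoring rule.

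In the student survey, Section 4 is labelled a tertiary outcome. Item 4.1 asks "Have you ever been to Indian Health Service or Fort Peck Tribal Health for things like condoms, birth control, a pregnancy test" or an STD test, answered yes or no. Item 4.2 has a longer list of sources but asks "If you need to get condoms, birth control, a pregnancy test, or a sexually transmitted disease test, where would you go".

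**The concern.** The network that H3 credits with the gain is wider than the two agencies in item 4.1. If coordination works by linking a student to the county health department or a school nurse for contraception or a pregnancy test, the survey may have nowhere to record it. The item also has no count and no recall period, although the stated outcome includes frequency. At stake is whether the trial can test the contraception and pregnancy-test part of its service-use hypothesis, and whether a result on item 4.1 could properly be reported as SRH service use in general.

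**Working it through.** The plan states no figure for this point, so the check sets the survey items against the outcome they are meant to supply.

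**Step 1. Which items record past use of a service?**

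| Student survey item | What it asks | Past use of contraception or pregnancy-test services? |
|---|---|---|
| 4.1 | Ever been to Indian Health Service or Tribal Health | Yes, two agencies, yes/no |
| 4.2 | Where the student would go | No, hypothetical |
| 4.3 | Comfort when a provider raises the subject | No |
| 4.4 | "how satisfied or dissatisfied would you say you are with the birth control and STD information and services you have received" | No, and there is no never-used option |
| 4.5 | "How likely is it that you will seek birth control or STD services from a health care provider in the next year" | No, intention |
| 5.7, 5.10 | Contraception used during sex | No, behaviour with no source asked |
| 5.12 to 5.16 | HIV, STD and HCV tests, diagnoses and follow-up care, any provider | No |

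Item 4.1 is the only yes in the last column. The testing items do not name a provider, but a skip rule at item 5.1 sends students who report no intercourse past them.

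**Step 2. Who is misclassified on item 4.1?** Item 4.2 lists "Roosevelt County Health Department", the school nurse and Fort Peck Tribal Health as separate options, so the survey itself treats them as different places. A student who used only the county must answer no. A student who used the county and also Indian Health Service answers yes. The error is confined to students who used other sources exclusively.

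**Step 3. Can frequency be built?** No. Item 4.1 and the testing items are all lifetime questions without counts or dates. A yes at baseline stays yes however often the student later returns. Section 3.1.5 (Generalized linear mixed-effects models) plans continuous responses for the tertiary outcomes, but item 4.1 is binary.

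**Step 4. What would item 4.1 show?** Let d be the true rise, in percentage points, in students who have ever used any source. Let s be the share of those new users who went to Indian Health Service or Tribal Health. Let m be the percentage points of all students who had used only other sources before and have since gone to one of the two agencies.

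Observed rise = d × s + m

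The documents give none of these quantities. For an assumed d of 10 points:

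| s | Observed rise if m = 0 | m at which the observed rise equals the true rise, d × (1 − s) |
|---|---|---|
| 100% | 10 | 0 |
| 80% | 10 × 0.8 = 8 | 2 |
| 60% | 10 × 0.6 = 6 | 4 |
| 50% | 10 × 0.5 = 5 | 5 |
| 20% | 10 × 0.2 = 2 | 8 |

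Below the m in the last column item 4.1 understates the rise, and above it item 4.1 overstates it.

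**The case against.** The strongest reply is that item 4.1 may carry little weight. Section 6.3.2 explains the outcome mainly through testing and follow-up, and items 5.12 to 5.16 record these wherever they took place. A reader might infer that a student who answers no to item 4.1 is scored as a non-user and that the whole H3 service-use effect is biased toward zero. The documents do not support that: no scoring rule makes item 4.1 the outcome, and Step 4 shows the error can run either way. What remains is that no scoring rule can recover past use that was never asked about.

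A reader might also infer that movement of students from Indian Health Service to the county goes unseen as lost use. It does not: item 4.1 asks about ever, so those students still answer yes, and such movement is substitution rather than the increase that H3 predicts.

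The school-nurse example is weaker than the county one. The nurses come from a health promotion program that Section 7 attributes to the Fort Peck Tribes, so some students may count them as Tribal Health, although item 4.2 lists them apart.

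The tracking log collects quarterly agency counts of adolescent visits with SRH services, of HIV, chlamydia and gonorrhea tests, and of several contraceptive methods. These help describe the systems level. They are aggregates, have no separate line for condoms or pregnancy tests, and belong to a component that Section 2.3.5 says is analyzed qualitatively. They cannot feed a student-level model.

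**Conclusion.** The point holds within limits. For contraception and pregnancy-test services, actual past use is recorded only as lifetime contact with two agencies. Exclusive users of other sources are missed, increases among those already answering yes are invisible, and the frequency named in Table 2 and the registry text cannot be obtained from the student survey. Testing is captured at any provider, for students reporting intercourse.

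The size and direction of any bias are unknown, because the documents do not say what share of students use other sources. The figures in Step 4 rest on assumed values and only show how the item behaves. The outcome is tertiary, and the primary and secondary analyses are not affected.

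**What to change.** **Before baseline.** Add one item asking, for each source already printed in item 4.2, how many times the student actually obtained these services there within a fixed recall window matched to the survey interval. Surveys fall at baseline, 3, 9 and 12 months, so the intervals are 3, 9 − 3 = 6 and 12 − 9 = 3 months. A 3-month window would give comparable counts at every survey, but would leave months 3 to 6 uncovered. State which items form the outcome and how they are scored. Define H3 service use as any use and number of uses across all sources, together with the testing items. The cost is a somewhat longer survey and a review-board modification.

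**If baseline was already collected with the printed wording.** Section 4.1 schedules it for mid-March to June 2019, and the appendices hold board memoranda from 2020, so this case may apply. Keep item 4.1 unchanged for the H3 model. Report it as use of Indian Health Service or Tribal Health only, not as SRH service use overall. Remove frequency from the stated H3 measure. A new item can still be added, but only as descriptive. Under Section 2.3.5, clusters are next surveyed after they start the intervention, so the item would have no control-period value and no intervention effect on it could be estimated.
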